6. STUDY OBJECTIVES AND ENDPOINTS

Primary Objective	Primary Endpoint
The primary objective of the study is to assess the safety impact of continuing aducanumab dosing in asymptomatic ARIA in subjects with MCI due to AD or with mild AD dementia.	The primary endpoint that relates to this objective is the incidence of clinically impactful ARIA, defined as symptoms and/or signs associated with ARIA that are life-threatening, require hospitalization, and/or result in persistent or significant disability as assessed by the independent Adjudication Committee.
Secondary Objectives	Secondary Endpoints
To characterize ARIA, from both the imaging and the clinical perspective	
Endpoints that relate to this objective include:
 
 • Incidence, severity, time to onset, and time to resolution of ARIA as obtained on MRI • Incidence, severity, time to onset, and time to resolution of symptomatic ARIA
To characterize the safety, tolerability, PK, and immunogenicity of aducanumab	
Endpoints that relate to this objective include:
 
 • Incidence of AEs and SAEs • Change from baseline to Week 54 on the MoCA • Aducanumab concentration in serum • Incidence of antiaducanumab antibodies in serum
Long-Term Extension Objectives	Long-Term Extension Endpoints
The primary objective of the LTE is to evaluate the long-term safety and tolerability profile of aducanumab in subjects with MCI due to AD or mild AD dementia while continuing dosing during asymptomatic ARIA events.	The endpoint that relates to this objective is the incidence of AEs and SAEs.

CONFIDENTIAL

The information contained herein may not be used, disclosed, or published without the written consent of Biogen MA Inc.

Any additional samples that are collected under separate optional consent may be used for future scientific and genetic research. Objectives related to this future research have not been determined.

CONFIDENTIAL

The information contained herein may not be used, disclosed, or published without the written consent of
Biogen MA Inc.

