moderate asymptomatic ARIA cases only. It is planned that dosing will be continued in severe ARIA cases as well (in Stage 2), contingent on the recommendation of the Data Safety Monitoring Committee (DSMC) following a review of the Stage 1 data (see Section 19.2.2 for additional details).

Study Objectives and Endpoints: The primary objective of the study is to assess the safety impact of continuing aducanumab dosing in asymptomatic ARIA in subjects with MCI due to AD or with mild AD dementia.

The primary endpoint that relates to this objective is the incidence of clinically impactful ARIA, defined as symptoms and/or signs associated with ARIA that are life-threatening, require hospitalization, and/or result in persistent or significant disability, as assessed by the independent Adjudication Committee.

Secondary objectives and endpoints are as follows:

- To characterize ARIA, from both the imaging and the clinical perspective:
 - Incidence, severity, time to onset, and time to resolution of ARIA as obtained on MRI
 - Incidence, severity, time to onset, and time to resolution of symptomatic ARIA
- To characterize the safety, tolerability, pharmacokinetics (PK), and immunogenicity of aducanumab:
 - Incidence of adverse events (AEs) and serious adverse events (SAEs)
 - Change from baseline to Week 54 on the Montreal Cognitive Assessment (MoCA)
 - Aducanumab concentration in serum
 - Incidence of antiaducanumab antibodies in serum

Long-Term Extension Objectives and Endpoints

The primary objective of the long-term extension (LTE) is to evaluate the long-term safety and tolerability profile of aducanumab in subjects with MCI due to AD or with mild AD dementia while continuing dosing during asymptomatic ARIA events.

CONFIDENTIAL

The information contained herein may not be used, disclosed, or published without the written consent of Biogen MA Inc.

The endpoint that relates to this objective is the incidence of AEs and SAEs.

Study Design: This is a Phase 2, multicenter, randomized, parallel-group, double-blind, controlled study with a 52-week randomized treatment period followed by an optional 104-week LTE period.

Study Location: Approximately 95 sites globally are planned.

Number of Planned Subjects: Approximately 500 subjects will be enrolled.

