Group 1	Continue dosing at current dose and schedule	Suspend dosing and receive placebo . Once ARIA-E resolves, subject may resume dosing at same dose.			
Group 2	Continue dosing at current dose and schedule ¹				
Symptomatic	Throughout Study, Groups 1 and 2				
Mild	Suspend dosing. Once ARIA-E and clinical symptoms resolve, the subject may resume dosing at the same dose.				
Moderate					
Severe					
Serious “other medically important event” only²					
Serious “hospitalization” only	Suspend or permanently discontinue treatment at treating HCP’s discretion				
Serious, except for “other medically important event” and “hospitalization”³	Permanently discontinue treatment				

¹In Group 2, dosing initially (Stage 1) will be continued in mild and moderate cases only. Following a review of the data and contingent on recommendation from the DSMC (i.e., in Stage 2), dosing will be continued regardless of MRI severity (as described in Sections 7 and 19.2.2). The only exception is a subject who has severe asymptomatic ARIA-E in Stage 1 and who develops recurrent asymptomatic severe ARIA-E in Stage 2; in this case, the subject will follow the Group 1 treatment paradigm, i.e., suspend active dosing and, after ARIA-E resolves, resume dosing at the same dose.

²“Other medically important events” requiring dose suspension include SAEs that are not life-threatening (in the opinion of the Investigator), do not require inpatient hospitalization or prolongation of existing hospitalization, and do not result in significant/permanent disability or congenital anomalies/fetal defects, but that may (in the opinion of the Investigator) jeopardize the subject or may require intervention to prevent one of the outcomes listed above and as described in Section 15.1.

³SAEs requiring permanent discontinuation of study treatment include those that are life-threatening (in the opinion of the Investigator) and/or that result in persistent or significant disability/incapacity or a congenital anomaly/birth defect, as described in Section 15.1.

CONFIDENTIAL

The information contained herein may not be used, disclosed, or published without the written consent of Biogen MA Inc.

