15.1.2. Serious Adverse Event

An SAE is any untoward medical occurrence that at any dose:

- Results in death
- In the view of the Investigator, places the subject at immediate risk of death (a life-threatening event); however, this does not include an event that, had it occurred in a more severe form, might have caused death
- Requires inpatient hospitalization or prolongation of existing hospitalization
- Results in persistent or significant disability/incapacity

CONFIDENTIAL

The information contained herein may not be used, disclosed, or published without the written consent of Biogen MA Inc.

- Results in a congenital anomaly/birth defect
- Is a medically important event

A medically important event is an AE that, in the opinion of the Investigator, may jeopardize the subject or may require intervention to prevent one of the other outcomes listed in the definition above. (Examples of such medical events include allergic bronchospasm requiring intensive treatment in an emergency room or convulsions occurring at home that do not require an inpatient hospitalization.)

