15.3.4.1. Deaths

Death is an outcome of an event. The event that resulted in death should be recorded on the appropriate CRF. All causes of death must be reported as SAEs within 24 hours of the site becoming aware of the event. The Investigator should make every effort to obtain and send death certificates and autopsy reports to Biogen. The term death should be reported as an SAE only if the cause of death is not known and cannot be determined.

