16.7. Sample Size Considerations

Based on the data from Study 221AD103, 2 out of 185 subjects (1%) experienced serious ARIA events resulting in hospitalization within the first 12 months of treatment with aducanumab. In addition, there were no deaths or persistent significant disability due to ARIA. Of the 185 subjects, 31 subjects were in the 10 mg/kg titration group, and none of them experienced clinically impactful ARIA. By applying the current definition of clinically impactful events as the primary endpoint to this study, a low incidence of clinically impactful ARIA events is expected to be observed during the study.

This is an estimation study. No formal hypothesis testing is planned. In Study 221AD103, of the 185 subjects, 20 subjects developed asymptomatic moderate ARIA-E and 1 subject developed severe asymptomatic ARIA-E. In order to enroll 25 subjects with asymptomatic moderate to severe ARIA-E in each treatment group, a sample size of approximately 500 subjects is selected to provide a preliminary estimate of incidence rates. The sample size may be re-estimated based on evolving learning from external sources and blinded review of this study. Subjects will be randomized in a 1:1 ratio to each of the 2 treatment groups. When 1 clinically impactful ARIA event is observed, the incidence rate will be 0.004 and the 90% exact CI will be (0.0002, 0.0188). If 2 events are observed, the incidence rate will be 0.008 and the 90% exact CI will be (0.0014, 0.0250), and if 3 events are observed, the incidence rate will be 0.012 and the 90% exact CI will be (0.0033, 0.0307).

CONFIDENTIAL

The information contained herein may not be used, disclosed, or published without the written consent of Biogen MA Inc.

The assumed incidence rates and the probability of observing events in each group are presented in the following table.

Incidence Rate in Group 1	Incidence Rate in Group 2	Probability of Observing Same Number of Events in Group 1 and Group 2	Probability of Observing at Least 1 More Event in Group 2 vs. Group 1	Probability of Observing at Least 2 More Events in Group 2 vs. Group 1	Probability of Observing at Least 3 More Events in Group 2 vs. Group 1
1%	1%	18%	41%	24%	13%
1%	2%	10%	77%	64%	49%
1%	3%	3%	93%	87%	79%

CONFIDENTIAL

The information contained herein may not be used, disclosed, or published without the written consent of
Biogen MA Inc.

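### Does the primary endpoint leave out ARIA that prolongs a hospital stay, or ARIA that proves fatal?

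*Protocol*

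**What the plan says.** Section 6 of the protocol defines the primary endpoint by three criteria: "symptoms and/or signs associated with ARIA that are life-threatening, require hospitalization, and/or result in persistent or significant disability". The Synopsis has the same three and, like Section 6, leaves the judgement to an independent committee: "that are life-threatening, require hospitalization, and/or result in persistent or significant disability, as assessed by the independent Adjudication Committee". Neither place mentions prolonging a stay or death, and neither points to the serious adverse event definition.

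Section 15.1.2, which defines serious adverse events, words the hospital criterion more fully: "Requires inpatient hospitalization or prolongation of existing hospitalization". It lists death as its own item, and it calls an event life-threatening when, in the Investigator's view, it "places the subject at immediate risk of death (a life-threatening event" (a caveat follows). The footnotes to Tables 5 and 6 also pair the two hospital situations, describing the medically important category as events that "do not require inpatient hospitalization or prolongation of existing hospitalization".

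Section 19.2.1 sends every symptomatic ARIA, and every ARIA reported as a serious adverse event, to the Adjudication Committee, and leaves detailed guidance to a charter that is not among the documents. Section 2.5.2.2 of the SAP records that the committee had not been formed when the study was terminated, and that the endpoint will not be evaluated.

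**The concern.** Hospitalization is the criterion most likely to produce events. The planning text in Section 16.7 reports that "2 out of 185 subjects (1%) experienced serious ARIA events resulting in hospitalization" in the earlier study, and adds that "there were no deaths or persistent significant disability due to ARIA". About the same rate was expected here, so each group would have had two or three events. With counts that small, one case ruled in or out shows in the result.

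The protocol uses the longer hospital wording in three places (Section 15.1.2 and the footnotes to the two tables) and the shorter wording in the endpoint. A strict reader could take the difference as deliberate. A subject already admitted for something else whose stay is extended by symptomatic ARIA would then not count. On the same reading, death would be excluded because it is a separate item in Section 15.1.2 and is not named in the endpoint.

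**Working it through.** **Prolonged stay**

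1. The endpoint speaks of symptoms or signs that make hospitalization necessary. It does not say admission, or new admission. If ARIA symptoms keep an inpatient in hospital, hospitalization is required because of them.
2. Tables 5 and 6 divide serious symptomatic ARIA into three rows: medically important only, hospitalization only, and the remaining serious events. The footnote for the first row excludes prolongation. The footnote for the last row names life-threatening events, disability or incapacity, and congenital anomaly, but not prolongation. The natural place left is the hospitalization row, so the protocol uses that one word for both situations.
3. The endpoint shortens other wording too: Section 15.1.2 has disability or incapacity, the endpoint has disability. This looks like abbreviated seriousness criteria and not a different scope.

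**Death**

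1. A fatal ARIA placed the subject at immediate risk of death. The caveat in Section 15.1.2 removes only events that would have had to be more severe to kill.
2. Section 15.3.4.1 says: "Death is an outcome of an event". The event behind the death is what is classified, and that event is life-threatening.
3. Section 16.7 reports the absence of ARIA deaths just before it applies the endpoint definition to the earlier study, so fatal cases were in view.

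**Size**

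Inputs: about 500 subjects randomized 1:1, so 500/2 = 250 per group, and a planning rate of 1% (Section 16.7, from 2/185 = 0.0108).

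The plan's own intervals come first. The exact 90% limits for x events in n = 250 are the 5% quantile of Beta(x, n − x + 1) and the 95% quantile of Beta(x + 1, n − x).

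| Events | Rate | 90% exact CI | Section 16.7 |
|---|---|---|---|
| 1 | 0.004 | 0.0002 to 0.0188 | same |
| 2 | 0.008 | 0.0014 to 0.0250 | same |
| 3 | 0.012 | 0.0033 to 0.0307 | same |

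One event is worth 1/250 = 0.4 percentage points in a group. At 2 events the interval is 2.50 − 0.14, or about 2.4 points wide.

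Expected events in the study: 500 × 0.01 = 5. Let q be the share of otherwise qualifying events that a narrow reading would leave uncounted. The documents give no value for q, so a range is assumed. The expected loss is 5q events, and each group's expected rate falls by 0.01q.

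| q (assumed) | Events lost, whole study | Fall in each group's rate |
|---|---|---|
| 1% | 0.05 | 0.01 points |
| 2% | 0.10 | 0.02 points |
| 5% | 0.25 | 0.05 points |

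**The case for a change.** The best argument for a change is that the inclusive reading is inferred and nowhere stated. Section 15.1.2 puts the life-threatening judgement with the Investigator, whereas the endpoint is judged by an independent committee, and Section 19.2.1 separates adjudication from adverse event collection and analysis. The seriousness definitions therefore do not carry over to the endpoint automatically. The unseen charter may or may not fill the space, and a cross-reference would cost one phrase.

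The factual part of this stands: the two wordings differ, and the endpoint cites no definition. The footnotes for the last row of Tables 5 and 6 are also phrased as inclusive lists, so the reading of those tables is strong but not a formal proof. The conclusion does not follow, though. Committee members who receive every relevant case, and who know how the protocol uses the word elsewhere, would have no good reason to exclude a prolonged stay or a fatal event. Scope questions at the level of single events are ordinary charter material. Section 16.2.2.1 also requires the primary endpoint events to be listed by group, so each counted event would be open to inspection.

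Copying the Section 15.1.2 wording into the endpoint would not be purely clarifying either. It would bring in the restriction to inpatient stays, which the endpoint does not now contain and which could narrow it.

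**Conclusion.** This is a difference in drafting that does not alter what the plan measures. The endpoint abbreviates the seriousness criteria, and the protocol's own usage supports counting both prolonged stays and fatal cases. Under assumed uncounted shares of 1% to 5%, the expected loss is at most a quarter of one event in the whole study, or 0.05 percentage points per group. The same definition applies to both groups, and nothing suggests a direction of bias. No figure in Section 16.7 would change.

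The conclusion rests on the 1% planning rate, on those assumed shares, and on the charter not contradicting the protocol. It has no bearing on the final report: the SAP leaves this endpoint unevaluated, while deaths are counted in the overall adverse event summary (SAP 2.5.1). A cross-reference to Section 15.1.2 would be an optional courtesy to anyone reusing the endpoint, and the plan is sound without it.

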4.3.2.1.3. Study 221AD103

Currently available data on ARIA are mostly based on the ongoing Study 221AD103 of aducanumab in subjects with prodromal AD or mild AD dementia. This study comprises a completed double-blind, 1-year placebo-controlled period, followed by an ongoing LTE in which all subjects receive aducanumab via monthly infusions, in a dose-blinded fashion. A total of 185 subjects have been dosed with aducanumab, in the placebo-controlled period and/or the LTE.

Based on data available as of 25 May 2017 in a prespecified interim analysis, ARIA-E (with or without ARIA-H) has been detected in 25% of all aducanumab-treated subjects (46/185). In the 12-month placebo-controlled period, in subjects receiving aducanumab in a fixed-dose regimen,

CONFIDENTIAL

The information contained herein may not be used, disclosed, or published without the written consent of Biogen MA Inc.

the incidence of ARIA-E increased with dose and was higher in ApoE ε4 carriers than noncarriers (3% [1/31], 6% [2/32], 37% [11/30], and 41% [13/32] in the 1, 3, 6, and 10 mg/kg dose groups, respectively). However, the incidence of ARIA-E appeared to be lower in ApoE ε4 carrier subjects receiving titration to 10 mg/kg (35% [8/23]) than in carrier subjects receiving fixed doses (43% [9/21] and 55% [11/20]) of 6 and 10 mg/kg, respectively. Furthermore, among the 8 ApoE ε4 carrier subjects receiving titration to 10 mg/kg who had ARIA-E, the abnormalities were observed at the 3 and 6 mg/kg dose levels (5 and 3 subjects, respectively).

The incidence of isolated ARIA-H was similar in the placebo and aducanumab groups (7% [3/46] and 5% [7/148], respectively), which likely indicates a background finding in this population.

ARIA was typically observed early in the course of the treatment, with the majority of cases observed between the second and fifth doses. A total of 91% of subjects (42/46) developed the first episode of ARIA-E within the first 12 months of active dosing, with 76% of subjects (35/46) developing the first episode within the first 6 months of active dosing. In most cases, ARIA-E resolved 4 to 12 weeks after onset as assessed by MRI, and ARIA-H was typically stable within 2 to 4 weeks after onset.

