14.1. Clinical Safety Assessments

The following clinical assessments will be performed to evaluate the safety profile of aducanumab:

- AE and SAE recording
- Brain MRI
- Physical examination, including height and weight
- Neurological examinations
- Vital sign measurements: temperature, heart rate, systolic and diastolic blood pressure, and respiratory rate
- 12-lead ECG
- Concomitant therapy and procedure recording
- Columbia Suicide Severity Rating Scale (C-SSRS)
 - The C-SSRS is a suicidal ideation and behavior rating scale used to evaluate suicide risk.
- MoCA for ARIA monitoring and management
 - The MoCA is a 30-point test widely used to detect cognitive dysfunction and is used in this study as a safety measure.

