16. STATISTICAL METHODS AND DETERMINATION OF SAMPLE SIZE

The objectives of the study and the endpoints to be analyzed are listed in Section 6. In general, study data will be summarized using standard descriptive statistics, and no formal statistical hypothesis testing is planned. Additional details of the analysis of study data will be provided in a separate Statistical Analysis Plan.

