16.2. Primary and Secondary Endpoint Analysis

16.2.1. Analysis Population

The safety population, defined as all subjects who were randomized and received at least 1 dose of aducanumab will be used for the primary and secondary endpoint analyses.

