16.2.2.2. Analysis of the Secondary Endpoints

The incidence of ARIA and their severity by imaging as well as clinical perspectives, will be summarized for each group and overall. These analyses will also be performed for the different types of ARIA (e.g., ARIA-E, ARIA-H). Kaplan-Meier plots will be produced to describe time to ARIA onset, time to symptomatic ARIA, and time to asymptomatic ARIA. Summary statistics will be presented to describe the time to resolution of ARIA.

The incidence of AEs, SAEs, and antiaducanumab antibodies, as well as clinical changes in vital signs and ECGs, will be summarized for each group and overall.

CONFIDENTIAL

The information contained herein may not be used, disclosed, or published without the written consent of Biogen MA Inc.

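### A Week 54 MoCA comparison in all dosed subjects is diluted six- to tenfold for dosing through asymptomatic ARIA; one small by-group table around the ARIA would help (minor)

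*Protocol*

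**What the plan says.** Protocol Section 6 lists "Change from baseline to Week 54 on the MoCA" as a secondary endpoint, under the objective on safety, tolerability, PK and immunogenicity. Section 16.2.1 says the safety population (randomized, at least one dose) "will be used for the primary and secondary endpoint analyses". Section 14.1 gives the scale's role as "MoCA for ARIA monitoring and management".

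Section 16.2.2.2 covers ARIA incidence, severity and timing, and then "The incidence of AEs, SAEs, and antiaducanumab antibodies, as well as clinical changes in vital signs and ECGs". It does not mention the MoCA at all, neither the Week 54 change nor scores around ARIA. Section 16 adds: "Additional details of the analysis of study data will be provided in a separate Statistical Analysis Plan".

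For the randomized period, MoCA collection around ARIA is supported by Sections 7.2.1 and 7.2.2 (who may perform it, including when ARIA is being managed) and by Section 11.2.4 (MRI and MoCA after ARIA has resolved or stabilized).

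The only SAP supplied was written after termination. It lists MoCA scores, places the totals beside the MRI assessments of participants with ARIA (2.5.3), and defines a differential study treatment population (2.3). It plans no MoCA summary by group.

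**The concern.** The trial asks whether it is safe to keep dosing through asymptomatic ARIA. A subject with no such ARIA has the same dosing plan in either group, so can contribute only noise to a group difference in MoCA. A comparison at Week 54 in everyone averages a possible effect in a small minority over a large majority, usually months after the episode. A Week 54 difference close to zero could then be read as reassurance about cognition during dosing through ARIA when it could hardly have shown otherwise. The MoCA scores taken around the ARIA bear on that question more directly, and the protocol names no group summary of them.

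**Working it through.** The documents give no precision or power figure for the MoCA, so there is none to reproduce. The planning share can be reproduced: Section 16.7 wants 25 subjects per group with asymptomatic moderate to severe ARIA-E out of about 500 randomized 1:1, and 25/250 = 10%.

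**1. Share of each group whose dosing can differ**
- Planning target: 25/250 = 0.100.
- Study 221AD103 rate (Section 16.7): (20 + 1)/185 = 0.114.
- Table 6 also separates the groups for moderate asymptomatic ARIA-H. Section 4.3.2.1.3 reports: "The incidence of isolated ARIA-H was similar in the placebo and aducanumab groups (7% [3/46] and 5% [7/148], respectively". Adding all of the aducanumab cases gives 0.114 + 7/148 = 0.114 + 0.047 = 0.161, or about 40 of 250. This is generous, because mild ARIA-H is managed alike in both groups.
- In Stage 1 only moderate cases differ, which lowers the share.

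Dilution = 1/share: 1/0.161 = 6.2 to 1/0.100 = 10. It does not depend on any assumed SD.

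**2. Timing**

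In Study 221AD103 first ARIA-E came early, "with 76% of subjects (35/46) developing the first episode within the first 6 months of active dosing". On duration: "In most cases, ARIA-E resolved 4 to 12 weeks after onset as assessed by MRI". Gap from the end of an episode to Week 54:

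| Episode starts | 12 weeks long | 24 weeks long |
|---|---|---|
| Week 16 | 54 − 28 = 26 weeks | 54 − 40 = 14 weeks |
| Week 26 | 54 − 38 = 16 weeks | 54 − 50 = 4 weeks |

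The 24-week column is a sensitivity case. Study 221AD103 suspended or stopped dosing for moderate or severe ARIA, and Section 4.4 reports shorter bapineuzumab episodes after discontinuation, so episodes that are dosed through may last longer.

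**3. What each comparison could show**

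Assumptions, not in the documents: SD of MoCA change 3 points (range 2 to 4); between-group loss in affected subjects of 2, 1 or 0.5 points. The 90% level follows Section 16.2.2.1.

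Half-width = t(0.95, 2n − 2) × SD × √(2/n).
- n = 25: 1.677 × 3 × √(2/25) = 1.42 points (0.95 to 1.90 for SD 2 to 4).
- n = 250: 1.648 × 3 × √(2/250) = 0.44 points (0.29 to 0.59).

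At Week 54 a lasting loss d in affected subjects becomes share × d. For d = 2 that is 0.20 to 0.32 points, smaller than the half-width of 0.44. The chance that the 90% interval lies wholly on the side of a loss (noncentral t, SD 3) is:

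| Loss in affected subjects | 25 v 25 around ARIA | 20 v 20 | 40 v 40 | Week 54, 250 v 250, share 10% to 16% |
|---|---|---|---|---|
| 2 points | 75% | 67% | 91% | 18% to 33% |
| 1 point | 31% | 27% | 43% | 10% to 15% |
| 0.5 points | 14% | 13% | 18% | 7% to 9% |

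For SD 2 and SD 4, a 2-point loss shows in 97% and 54% at 25 v 25, against 30% to 56% and 14% to 23% at Week 54. A loss that has resolved by Week 54 shows there only at the chance level of 5%.

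**4. Is a MoCA available about 12 weeks after the scan?**

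Scheduled MRI visits (Weeks 16, 24, 32, 44, 54) fall 8 and 16 weeks after Week 16, and 8 and 20 weeks after Week 24. None lies 10 to 14 weeks after either. ARIA visits run every 4 weeks, but only until resolution or stabilization. Section 11.2.4 then adds a MoCA 2 weeks after the second dose. Counting the dose at the resolution visit as the first, ARIA that resolves 4 weeks after the scan gives a MoCA at about 8 + 2 = 10 weeks, and ARIA that resolves at 8 weeks gives one at about 12 + 2 = 14. Unresolved cases have an ARIA visit at 12 weeks. Most subjects should therefore have a score in or near the window.

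**The case against.** The strongest reply is that Week 54 MoCA was never assigned to this question. It sits under general safety. The protocol names a between-group difference only for the primary endpoint, and dosing through ARIA is judged by adjudicated clinically impactful ARIA and by symptomatic ARIA. A decline judged symptomatic enters those endpoints. A late MoCA in everyone dosed suits a question about lasting effect. This stands: the Week 54 endpoint is reasonable and should stay.

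A reader might infer that the protocol rules out any analysis of MoCA around ARIA, or that the SAP is at fault. The documents support neither. Section 16.2.2.2 is silent on every MoCA analysis and detail is deferred to a SAP. The endpoint list is open and some text is redacted. The one SAP supplied was written for a terminated trial with little data, and it already pairs MoCA with MRI for participants with ARIA. Those are listings, however, not a group comparison.

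A reader might also take Tables 2 and 3 as proof of MoCA at ARIA visits in the randomized period. They cover the extension, where all subjects follow Group 2 rules, so they cannot feed a by-group table. Table 1's columns are broken in the text supplied, so its ARIA visit has to be confirmed.

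Two cautions about the remedy also stand. If episodes are shorter in one group, missing 12-week scores and practice effects may be unequal. And about 25 per group would usually miss losses of 0.5 to 1 point.

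**Conclusion.** The point holds as a minor, inexpensive improvement to the protocol as planned. With 10% to 16% of each group open to different dosing, a Week 54 group difference is diluted about six- to tenfold, and for early ARIA-E it usually comes weeks to months after the episode. It can address a lasting average effect, but says little about subclinical change during dosing through ARIA. The dilution rests only on the protocol's own counts. The detection probabilities rest on an assumed SD and assumed losses. The gaps of 16 and 26 weeks are illustrations; a reader might take them as minimums, but they come from a study that suspended or stopped dosing for moderate or severe ARIA. Since the trial was terminated, the value lies in the design as planned or in a successor study.

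**What to change.** Keep the Week 54 endpoint. Add to Section 16.2.2.2 one descriptive table of mean MoCA change by randomized group, with the group difference and 90% CI:

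- **Who:** subjects with a first asymptomatic ARIA that the groups manage differently (moderate in Stage 1; moderate or severe in Stage 2; ARIA-E or ARIA-H, excluding macrohemorrhage). Fix membership at the qualifying scan. This is close to the SAP's differential study treatment population.
- **Reference:** the last MoCA before the first infusion that could differ between groups.
- **Time:** about 12 weeks after the scan, window 10 to 14, whether or not the ARIA has resolved. Use ARIA visits if unresolved and Section 11.2.4 MoCAs if resolved. Do not compare lowest scores, because longer episodes give more visits and lower minima by chance.
- **Collection:** confirm that the Table 1 ARIA visit includes the MoCA and add it if not. State that it is done before any infusion at that visit; footnote 9 as printed is attached to Day 1 eligibility and ApoE genotyping and does not clearly cover later visits. If no score falls in the window, collect one at the 12-week dosing visit, or at an equivalent visit for subjects moved to Table 4, which schedules no MoCA outside ARIA visits.
- **Report by group:** number with data, resolution status and number of prior MoCAs, so that unequal missing data or practice effects can be seen.

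The cost is one small table, mostly from scores already planned if the Table 1 visit is confirmed, plus an occasional extra MoCA. The interval will be wide: about ±1.4 points at 25 per group with SD 3. Where the reference score is as old as Day 1 this should add noise rather than bias, because both groups are dosed alike up to the qualifying scan.
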